Patients undergo frequent bronchoscopy in the weeks and months following lung transplantation. Many, if not most patients develop some element of necrotic desquamation of the epithelium locally referred to as “exudative plaques” or “pseudomembranes” in the large central airways two to four weeks after lung transplantation. There is a spectrum of involvement, but prior work would suggest that up to 50% of patients who develop the most severe manifestations of these plaques go on to develop some form of large airway complication, most commonly CAS⁹. Our local experience supports this observation. There is no established intervention available for these patients, however, because airway ischemia is thought to play an important role in this process, our group has treated a small group of patients with hyperbaric oxygen therapy (HBOT) with anecdotal improvement in the appearance of the airways as well as a perceived reduction in frequency and severity of anticipated airway complications in some patients.

HBOT is defined as compression of the body with at least 1.4 atmospheres absolute pressure (ATA) of pure oxygen. It is believed to decrease inflammation, control infection, enhance perfusion and promote wound healing.¹⁰ It is used for treatment of chronic refractory wounds, including diabetic, small arterial and radiation-related wounds, as an adjunct to surgical reconstruction wounds, flaps or grafts, and chronic osteomyelitis.¹¹⁻¹³ It has been shown to improve wound healing and decrease the need for limb amputations in diabetic patients. HBOT is not necessary or recommended for normal or uncompromised grafts or flaps, but where the graft or flap is compromised by hypoxia, ischemia or congestion, HBO₂ has been shown to be extremely useful in graft salvage (14). Our preliminary experience with HBOT in lung transplant patients with severe pseudomembranes has been encouraging. We perceive that use of this technique has hastened resolution of the pseudomembranes, improved infectious complications and decreased the incidence of CAS. Based on this preliminary experience we feel systematic examination of this approach is warranted.

OBJECTIVES:

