The objective of this study is to evaluate the effect of HBOT on subsequent airway complications in lung transplant recipients with evidence of ischemic changes in the large airway epithelium. Study subjects with extensive desquamation (exudative plaques) of the large airway epithelium in the early post-transplant period will be randomized to HBOT or usual care and followed clinically for 12 months following randomization. We hypothesize that HBOT will decrease the number of airway complications in the treated subjects.

SUBJECT ENROLLMENT

Standard post-lung transplantation care includes a bronchoscopy with transbronchial lung biopsy at 1 month after surgery. We believe that it is in this early period, when the neovascularization of the large airways is thought to occur, that subjects are most likely to benefit from HBOT. Patients who are noted to have extensive exudative plaques (grade 3 or 4) at their 1 month bronchoscopy will be referred for a standard follow-up bronchoscopy 2 to 3 weeks later. Should the patient show no sign of improvement in their airways, or worsening of the plaques they will be considered eligible for enrollment in the study.

Exclusion Criteria

Exclusion criteria include: use of mechanical ventilation with FiO₂ greater than 40%, use of extracorporeal membrane oxygenation, use of inhaled nitric oxide, presence of pneumothorax, pregnancy, or inability to provide informed consent. In addition, subjects who are deemed to be

too clinically unstable to be transported safely to the hyperbaric facility by their treating physicians will be excluded from enrollment.

Randomization

Once subjects are deemed eligible for enrollment, they will be questioned as to their interest in participating in the study by the treating physician. Those interested will be approached by the study coordinator for informed consent. Once informed consent is obtained, subjects will be randomized to usual care or HBOT by selection of a pre-prepared envelope containing the randomization assignment. We will target a total enrollment of 40 subjects with 1:1 enrollment to either HBOT or usual care.

Subject Compensation

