While the patients randomized to receive usual care will not undergo HBOT, both study groups will receive standard serial bronchoscopies for airway clearance and for the collection of bronchoalveolar lavage fluid for culture data, due to the high rate of infection in lung transplant patients. All subjects will undergo the standard surveillance bronchoscopies every 3 to 4 weeks (x3) for clearance of the exudate from the airway, as well as monitoring progression of the airway abnormalities. Additional bronchoscopies will be performed as clinically indicated. Following the completion of the airway surveillance, subjects will revert to the standard rejection surveillance schedule of bronchoscopy every 3 months for the first year post-transplant.

At each surveillance bronchoscopy, subjects will have the standard bronchoalveolar lavage performed for detection of infectious agents. Due to the high evidence of airway infections in patients with severe exudative plaques, a lavage is performed during each bronchoscopy as a part of standard practice to collect microbiologic data. As participants in this study, an, endobronchial biopsy of the airway epithelium will be performed at the main carina to collect a sample of recipient epithelium as well as at the first subcarina for each donor lung. Three samples will be collected from each of the biopsy sites. These samples are small (1 to 2 mm) and are thought to have a minimal clinical risk of minor bleeding associated with the procedure. Biopsy will add roughly 3 minutes total to each procedure. These samples will be used for mRNA extraction to detect expression of genes associated with response to tissue hypoxia.

Measurements and Data Collection

Primary outcomes: Need for airway stent placement and rate of acute rejection in the 12 months of observation as determined by transbronchial lung biopsy.

Secondary outcomes: Include development of airway stenosis, need for balloon bronchoplasty, development of clinically significant pulmonary infection as defined by initiation of antimicrobials to treat the suspected organism, development of airway dehiscence following enrollment in the study, development of bronchiolitis obliterans syndrome, and bronchial epithelial gene expression.

Additional clinical data to be collected will include spirometric data, frequency of hospitalization, hospital days, ICU days, mechanical ventilation days, need for tracheostomy, and survival.

TREATMENT ARM CROSSOVER

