Should patients enrolled in the usual care arm develop airway complications such as airway stenosis, dehiscence, or airway malacia, or if the patient fails to improve their exudative plaque score over the period of observation, they may be offered hyperbaric therapy with continued collection of clinical data. Subjects will be eligible for crossover therapy between 8 and 12 weeks after the initial study bronchoscopy.

There are two criteria for a patient to qualify for HBOT crossover treatment. The first criterion is the development of an airway complication, most likely airway stenosis requiring intervention. This is clinically defined by our group as an airway that is no longer traversable with a therapeutic (6.4mm OD) bronchoscope. Other complications are airway dehiscence or malacia (excessive loss of structural integrity). The second criterion is failure of the airway exudate to improve in score severity during the 8 week observation period. This is measured using the scoring system outlined in Table 1.

RISK/BENEFIT ASSESSMENT

It is currently unknown if treatment of patients with severe exudative plaques in the early post-lung transplant period with HBOT will prevent development of large airway complications. Our limited anecdotal experience suggests it may improve outcomes. The risks of the procedure are small and detailed above. The potential benefits are significant since airway stenosis can lead to worse allograft function, increased infections, and occasionally death. Subjects randomized to usual care will be at usual risk of airway complications. Given the clinical equipoise regarding HBOT treatment in lung transplant, we feel this is an ethical treatment decision for this patient population.

COST TO THE SUBJECT

There will be no additional costs to the subject over usual care. The hyperbaric treatment will be provided at no charge to the subjects.

DATA ANALYSIS AND STATISTICAL CONSIDERATIONS

Data analysis will be performed by the primary investigators. Categorical data will be analyzed using Fisher's exact test given the small sample size, while continuous data will be assessed for statistical significance with Student's t-test. Our prior work with airway stenosis in lung transplant recipients documented a 15% rate of stenosis in all transplant patients. Our clinical experience suggests a rate 2 to 4-fold higher in patients with severe ischemic desquamation of

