the large airways. Experience with HBOT in this population is limited, but rates of significant airway stenosis may be as low as 10% after therapy. Sample size calculations using a 60% stenosis rate in the usual care group, a 10% stenosis rate in the HBOT group with a p-value of 0.05 suggest that a sample of 14 subjects/group will have an 80% power to detect statistical significance. We will target a total of 40 subjects to allow for subject withdrawal and loss due to the development of critical illness in this tenuous population. Intention to treat analysis will be used for all patients based on initial randomization, with subgroup analysis for the crossover patients for airway stent placement. All biologic samples will be collected by week 6, prior to any patient crossover events.

DATA and SAFETY MONITORING

Data will be stored on a secured Access database located on the PIN station “U” drive in an secured folder. All subject entries will be de-identified using a study assigned identification number. The key to the study identifiers will be kept in a locked file cabinet in the study coordinators office. Database use will be limited to the primary investigators, co-investigators, and the study coordinator.

Primary risks are related to bronchoscopy with minimal risk of bleeding related to the endobronchial lung biopsy, and some discomfort from the bronchoscopy itself which is part of usual post-transplant care. Additional risks of hyperbaric treatment are detailed above and very rare. Any adverse events that occur during the study will be immediately reported to the IRB.

Table 1. Pseudomembrane Scoring System

Stage	Definition
Stage 0	No exudate
Stage 1	Limited to anastomosis
Stage 2	Anastomosis to upper lobe orifice, including medial bronchus intermedius
Stage 3	Involvement of the lower lobe orifice
Stage 4	Covers all visible airways

REFERENCES:

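### The only power calculation is for airway stenosis, a secondary outcome; neither primary outcome has one, and the stated 80% is not reached by a two-sided Fisher test

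*Combined protocol and SAP*

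**What the plan says.** Measurements and Data Collection sets the hierarchy: "Primary outcomes: Need for airway stent placement and rate of acute rejection in the 12 months of observation as determined by transbronchial lung biopsy". The next paragraph puts stenosis one level down: "Secondary outcomes: Include development of airway stenosis, need for balloon bronchoplasty".

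Data Analysis and Statistical Considerations contains the only sample-size calculation. Its inputs are "Sample size calculations using a 60% stenosis rate in the usual care group, a 10% stenosis rate in the HBOT group" at a p-value of 0.05, and these "suggest that a sample of 14 subjects/group will have an 80% power to detect statistical significance". The same section chooses the test for categorical data, Fisher's "exact test given the small sample size", without saying whether it is one- or two-sided.

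The enrolment target is 40, or 20 per group (Randomization). It is presented as the calculated number plus a margin for losses: "We will target a total of 40 subjects to allow for subject withdrawal" and for critical illness.

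Two passages bear on the usual-care rate. The statistical section puts stenosis at 15% in all recipients and two to four times that in patients with severe desquamation. The Background reports that "up to 50% of patients who develop the most severe manifestations of these plaques go on to develop some form of large airway complication", and says that local experience agrees.

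**The concern.** The trial will be judged on stenting and rejection, and the plan states no chance of detecting an effect on either. A non-significant primary result could not be read against any planned effect, and a reader could easily carry the 80% over to outcomes it was never computed for.

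Stenosis cannot stand in for stenting. The Background says that stenosis is treated first by balloon dilation, with stents for recurrence, and balloon bronchoplasty is a separate secondary outcome. The statistical section speaks of significant stenosis, and Treatment Arm Crossover of stenosis that needs intervention. Those may lie nearer to stenting than any stenosis does, but they still include patients treated by dilation alone. Rejection is a different outcome, read from biopsy, and the stenosis rates say nothing about it.

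Even for stenosis, the 80% belongs to a different calculation from the test that will be run, and it uses the most favourable control rate in the plan's range.

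**Working it through.** **Inputs from the protocol.** Stenosis 60% (usual care) and 10% (HBOT); alpha 0.05, sides not stated; 14 per group for 80% power; Fisher's exact test; 20 per group targeted. Plan's range for the usual-care rate: 15% × 2 = 30% to 15% × 4 = 60%. Upper figure in the Background for any large airway complication: 50%.

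**Step 1: reproduce the 14.** Two-sided normal approximation with pooled variance and no continuity correction, mean rate (0.60 + 0.10)/2 = 0.35:

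n = [1.960 √(2 × 0.35 × 0.65) + 0.842 √(0.60 × 0.40 + 0.10 × 0.90)]² / (0.60 − 0.10)² = [1.322 + 0.483]² / 0.25 = 13.04, rounded up to 14.

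So 14 is not an arithmetic slip. This formula may be its source, but it is not the planned test.

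**Step 2: power under Fisher's exact test.** Power = Σ Bin(a; n, p₁) · Bin(b; n, p₂), summed over all tables (a, b) with Fisher p ≤ 0.05. Two-sided, stenosis:

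| Usual care vs HBOT | 14 per group | 17 per group | 20 per group |
|---|---|---|---|
| 60% vs 10% (the plan's case) | 74.2% | 82.7% | 90.8% |
| 50% vs 10% (Background's upper figure) | 53.6% | 62.6% | 74.2% |
| 30% vs 10% (bottom of the plan's range) | 13.7% | 18.6% | 24.2% |

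For 60% vs 10%, 15 per group gives 73.9% and 16 gives 78.6%, so 17 is the first size to reach 80%. One-sided Fisher at 0.05 gives 80.7% at 14.

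**Step 3: the margin for losses.** As presented, 20 − 14 = 6 of 20, or 30%. Under two-sided Fisher, 20 − 17 = 3 of 20, or 15%.

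**Step 4: the primary outcomes.** Their power cannot be computed, because the documents give no rates. The figures below rest on assumed rates and show only how much the answer depends on them (20 per group, two-sided Fisher).

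- *Stenting, with a fraction s of stenoses stented in both arms* (rates 0.60s vs 0.10s): s = 75% (45% vs 7.5%) gives 72%; s = 50% (30% vs 5%) gives 45%; s = 25% (15% vs 2.5%) gives 11%.
- *Crossover.* Usual-care patients may be offered HBOT 8 to 12 weeks after the initial study bronchoscopy and are analysed as randomized. If that lowered the usual-care stent rate by a relative 10%, 25% or 50%, the 72% becomes 61%, 43% or 16%, and the 45% becomes 36%, 23% or 7%. If crossover is rare or has no effect, nothing changes.
- *Rejection, if binary and halved by HBOT:* 40% vs 20% gives 19%; 60% vs 30% gives 35%. If rate means a count of episodes, these two figures do not apply.

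**The case against.** The plan attaches its 80% openly to stenosis and claims no power for a primary outcome. That is true, but it leaves the primary outcomes with no power statement at all, which is the main point.

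The Fisher shortfall is modest. The 14 follows from a standard formula, one-sided Fisher does reach 80%, and at 60% vs 10% the real target of 20 gives 91% and stays above 80% down to 17 evaluable per group. Under intention to treat, a withdrawal need not mean a missing outcome. This stands as a limit on size: the mismatch by itself does not sink the trial. The sentence is still wrong as written for a two-sided test, and a one-sided test would have to be declared.

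The 60% may be defensible. Enrolment requires grade 3 or 4 plaques at one month and no improvement two to three weeks later, which could select a group at higher risk than the one behind the 50%. So 60% is optimistic, not contradictory, but the plan does not make that argument.

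The stenting, rejection and crossover figures use inputs from outside the documents, and most of the stent scenarios lower power. That is fair, and the verdict does not rest on them.

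Finally, the trial's title names stenosis and its hypothesis concerns airway complications, so the outcome list may be as much at fault as the calculation. The two disagree either way.

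**Conclusion.** The concern holds, and it must be fixed. Nothing in the documents supports 80% power for stent placement or acute rejection. Their power is unknown, not shown to be poor.

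For stenosis at the plan's own rates, two-sided Fisher at 0.05 gives 74% at 14 per group, about 6 points below the stated figure. It takes 17 per group to reach 80%, which halves the loss margin from 30% to 15% in a population the plan itself regards as fragile. If 50% is the right usual-care rate, even full enrolment gives only 74%. The Fisher results assume equal groups and two sides; with one side, the 80% at 14 is met.

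**What to change.** Revise the sample-size paragraph in Data Analysis and Statistical Considerations:

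1. Say that the calculation is for stenosis, a secondary outcome, and is not a power claim for the primary outcomes.
2. State two-sided Fisher and replace the 80% at 14 per group by 74% at 14, 83% at 17 and 91% at 20; or declare the test one-sided (81% at 14). Add 50% vs 10% (54%, 63% and 74%), or explain why 60% is preferred, for instance through the selection at enrolment.
3. Give assumed 12-month stent rates by arm, allowing for crossover, and the Fisher power at the expected evaluable number. Do the same for rejection, saying whether it is binary or a count. For either outcome, a plain statement that the trial is not powered for it is an acceptable alternative. Say also how the two primary outcomes share alpha, since their power depends on it.

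Possible wording:

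> This calculation concerns airway stenosis, a secondary outcome. For stent placement we assume __% (usual care, allowing for crossover) and __% (HBOT), giving __% power with __ evaluable per group [or: the trial is not powered for this outcome]. For acute rejection: [rates and power] [or: the trial is not powered for this outcome].

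Making stenosis the primary outcome is a separate option for the sponsor, with its own trade-off, and is not needed for this fix.

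The cost is a few sentences, with no added patients, visits or procedures. The stated power becomes less favourable, and the sponsor must commit to rates that the documents do not now contain, or say that it cannot.

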EFFECT OF HYPERBARIC OXYGEN THERAPY ON THE DEVELOPMENT OF AIRWAY STENOSIS IN PATIENTS WITH SEVERE AIRWAY EXUDATIVE PLAQUES EARLY AFTER LUNG TRANSPLANTATION

[name], [name], [name]

NCT02363959

BACKGROUND:

Central airway stenosis (CAS) is seen in 8-15% patients after lung transplantation.^{1,2} Development of airway stenosis can cause decline in pulmonary function, increased respiratory symptoms, increased infections, and occasionally death³. The lungs are unique in containing dual circulatory supply from the pulmonary circulation which is reanastomosed during lung transplantation, and the bronchial circulation which is not. Perfusion of the large airways is thought to occur via retrograde flow from vascular plexus' between the bronchial and pulmonary arterial circulation until new collateral circulation to the bronchial arterial system can develop in the weeks following transplantation³. Assessment of large airways perfusion has been surprisingly poorly studied, but development of airways ischemia post-transplantation is thought to be involved with development of CAS and other airway complications, opportunistic infections, particularly fungal infections, and possibly with chronic allograft rejection.^{1,4}

CAS is managed with balloon dilation followed by airway stent placement for recurrent stenosis.⁴⁻⁷ A limited number of retrospective studies have shown that the treated airway complications do not affect survival.^{1,8} However, these airway complications prolong mechanical ventilation, hospital and ICU length of stay, increase cost, and adversely affect quality of life³.

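### The trial is sized on stenosis but its primary airway outcome is stent placement, so the stated 80% power does not apply to the primary airway comparison

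*Combined protocol and SAP*

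**What the plan says.** Measurements and Data Collection names two primary outcomes: "Primary outcomes: Need for airway stent placement and rate of acute rejection in the 12 months of observation". The earlier steps of airway disease are in the next list: "Secondary outcomes: Include development of airway stenosis, need for balloon bronchoplasty". The Background gives the order of those steps: "CAS is managed with balloon dilation followed by airway stent placement for recurrent stenosis".

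Data Analysis and Statistical Considerations sets one test for all yes/no outcomes: "Categorical data will be analyzed using Fisher's exact test given the small sample size". The power statement in that section concerns stenosis only. It begins "Sample size calculations using a 60% stenosis rate in the usual care group", continues "a 10% stenosis rate in the HBOT group with a p-value of 0.05", and concludes that "a sample of 14 subjects/group will have an 80% power to detect statistical significance". Target enrolment is 40, allocated 1:1, to allow for withdrawal and critical illness.

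No section gives an expected stent rate, the share of stenoses that go on to a stent, or a power for the stent comparison.

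**The concern.** The effect assumed for HBOT is on the first step of the sequence, stenosis. The primary airway test looks only at the last step. A patient dilated several times but never stented is scored as a patient whose airway never narrowed. Because stents are placed for recurrence after dilation, stents should be fewer than stenoses. With fewer events and the same relative effect, power is lower.

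At stake is whether the primary airway comparison can detect the effect the plan assumes. HBOT could reduce stenosis exactly as hoped, and the stent comparison could still miss 0.05 because the trial was never sized for it.

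**Working it through.** **Inputs from the protocol.** Stenosis 60% against 10%; alpha 0.05, with sidedness not stated (two-sided assumed here); 14 per group for 80% power; 40 enrolled 1:1, so 20 per arm before losses; Fisher's exact test.

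**Input not in the protocol.** The share f of stenoses that reach a stent. It is assumed equal in both arms and varied.

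**Step 1: the plan's own figure.** Pooled normal approximation, no continuity correction:

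n = [1.960·√(2·p̄·(1−p̄)) + 0.842·√(p₁(1−p₁) + p₂(1−p₂))]² / (p₁−p₂)², with p₁ = 0.60, p₂ = 0.10, p̄ = 0.35

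= [1.960·√0.455 + 0.842·√0.33]² / 0.25 = (1.322 + 0.483)² / 0.25 ≈ 13.04, rounded up to 14.

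The 14 per group is reproduced. With the planned test it falls a little short. Exact two-sided Fisher power for 60% against 10%, by full enumeration, is 74% at 14, 83% at 17 and 91% at 20 per group. The enrolment target covers this if losses are small.

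**Step 2: stent yes/no.** Stent rates are 0.60·f and 0.10·f. Power is the sum, over all pairs of stent counts with two-sided Fisher p ≤ 0.05, of the product of the two binomial probabilities.

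| Share f | Stent rates | Power, 20 per arm | Power, 14 per arm |
|---|---|---|---|
| 1.0 (same as stenosis yes/no) | 60% vs 10% | 91% | 74% |
| 0.9 | 54% vs 9% | 85% | 66% |
| 0.8 | 48% vs 8% | 77% | 56% |
| 0.7 | 42% vs 7% | 67% | 46% |
| 0.5 | 30% vs 5% | 45% | 24% |
| 0.3 | 18% vs 3% | 17% | 6% |

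By the formula of Step 1, 80% power for stent needs 19 per arm at f = 0.8 and 36 per arm at f = 0.5.

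**Step 3: alternatives from data already collected.** Stenosis yes/no is the first row of the table. For the worst airway state on four ordered levels (none, stenosis, balloon bronchoplasty, stent), a simulated rank test with the same severity split in both arms has about 93% power at 20 per arm and 78–83% at 14. The range at 14 reflects the exact and asymptotic versions of the test. These figures hardly depend on f.

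**Step 4: lower end of the plan's range.** The protocol puts the rate in this population at 2 to 4 times 15%, that is 30% to 60%, and sizes on the upper end. At 30% against 10% and 20 per arm, power is 24% for stenosis yes/no, about 29–36% for the ordered scale, and 2–14% for stent (f from 0.3 to 0.7).

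**Step 5: a case against the ordered scale.** Suppose HBOT prevents only progression: stenosis 60% in both arms, stent 30% against 5%. At 20 per arm the rank test has about 12% power and stent yes/no 45%. With stenosis 60% against 50% and the same stent rates, the figures are about 25% and 45%.

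**The case against.** A stent is a clinically weighty endpoint, and a sponsor may choose it without citing a guideline. The lower steps are not thrown away: stenosis and balloon bronchoplasty are named secondary outcomes with a planned test. The Background also reports a perceived reduction in both frequency and severity of complications, so an effect on progression to stent is plausible, and in that case stent yes/no is the better test (Step 5). All of this stands. It supports stent as a legitimate choice, but it does not supply a power calculation for it, and secondary reporting does not repair a primary comparison that was not sized.

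A reader might infer that most of the planned power is lost. The documents do not support that, because it depends on a stent share they do not give. At 20 per arm power is still 85% at a share of 0.9 and 77% at 0.8; it falls to about half of the 91% only near a share of 0.5.

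A reader might also credit the gain to the ordered scale. Nearly all of it comes from counting stenosis at all: 91% for stenosis yes/no against about 93% for the ordered scale.

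The equal-share assumption is itself open to question. Usual-care patients with an airway complication may be offered HBOT between 8 and 12 weeks and are still analysed as randomised. If later HBOT prevents stents in that arm, the stent difference shrinks further, whereas a stenosis that led to crossover has already been counted.

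**Conclusion.** The point holds as a mismatch between the sizing outcome and the primary airway outcome. The 80% power at 14 per group belongs to a secondary outcome, and the protocol offers no power for stent. Under the plan's own 60% against 10%, with a two-sided Fisher test at 0.05 and an equal stent share in both arms, stent power drops below 80% at 20 per arm once the share is about 0.8 or lower. At 14 per arm it is below 80% at every share. How far it falls cannot be settled from the documents: 77% at a share of 0.8, 45% at 0.5, 17% at 0.3. The calculations use the full 0.05 for stent, although acute rejection is listed as primary beside it with no rule for dividing alpha.

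Aligning the outcome does not rescue the trial at the lower end of its own assumed range. At 30% against 10% stenosis, none of the options is well powered.

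**What to change.** Align the primary airway analysis with the outcome on which the trial is sized. Either of two forms would do:

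- **Stenosis yes/no by 12 months**, using the bronchoscope-passage definition already given under Treatment Arm Crossover, with the planned Fisher test.
- **Worst airway state by 12 months** (none, stenosis, balloon bronchoplasty, stent), compared by an exact Wilcoxon rank-sum test. The protocol must then define the lowest stenosis level, because the existing definition covers only stenosis requiring intervention. It must also say where death, withdrawal, dehiscence and malacia are placed.

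In both cases, report the stent rate as a key secondary outcome and restate power for the chosen primary outcome with the test that will be used. If the sponsor prefers to keep stent as primary, the protocol should state the expected stent rates and the power they give.

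The cost is protocol and analysis wording plus, for the ordered scale, the definitions above. The components are already collected, and no patients or procedures are added. The downsides are that the ordered scale has a less familiar effect measure, and that it has less power than stent yes/no if HBOT acts only on progression from stenosis to stent.

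### The 1-month biopsy should give a pre-randomisation reading of the rejection outcome, but neither allocation nor analysis uses it, which costs precision and power

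*Combined protocol and SAP*

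**What the plan says.** All places are in the combined protocol and SAP.

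- **Baseline biopsy (Subject Enrollment).** "Standard post-lung transplantation care includes a bronchoscopy with transbronchial lung biopsy at 1 month after surgery". The same bronchoscopy screens for the trial: patients with grade 3 or 4 plaques "at their 1 month bronchoscopy will be referred for a standard follow-up bronchoscopy 2 to 3 weeks later", and only those without improvement become eligible. Randomisation therefore comes after the 1-month biopsy.
- **Exclusions (Exclusion Criteria).** The list covers "use of mechanical ventilation with FiO₂ greater than 40%, use of extracorporeal membrane oxygenation, use of inhaled nitric oxide, presence of pneumothorax, pregnancy", inability to consent and clinical instability. Rejection at 1 month is not on it.
- **Allocation (Randomization).** Patients are "randomized to usual care or HBOT by selection of a pre-prepared envelope containing the randomization assignment". The target is 40 patients, 1:1. No stratification is stated.
- **Outcome (Measurements and Data Collection).** The primary outcomes are need for an airway stent and the "rate of acute rejection in the 12 months of observation as determined by transbronchial lung biopsy". No rule limits rejection to new episodes. In the same section, one secondary outcome does carry a limit: "development of airway dehiscence following enrollment in the study".
- **Observation period (Objectives).** Patients are "followed clinically for 12 months following randomization".
- **Analysis (Data Analysis and Statistical Considerations).** "Categorical data will be analyzed using Fisher's exact test given the small sample size"; continuous data get Student's t-test. No covariate or stratified analysis is mentioned. The analysis is by intention to treat.

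**The concern.** The plan has, or should have, a pre-randomisation measurement of a primary outcome and makes no use of it. If rejection at 1 month predicts rejection later, two things follow in a trial of 40.

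First, a chance difference between the arms in prior rejection moves the crude comparison in the one trial that is run, and a reader of the unadjusted result cannot separate this from an effect of hyperbaric oxygen. Second, outcome variation that the 1-month result could explain stays in the noise, so power is lower than the same 40 patients could give. The protocol states no power for rejection at all: its sample size rests on stenosis, a secondary outcome.

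A lesser issue is one of definition. Because nothing limits the outcome to new episodes, a biopsy after randomisation that shows the 1-month episode still unresolved could be counted as an event.

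**Working it through.** **The plan's own figure.** The stated 14 per group (stenosis 60% vs 10%, alpha 0.05, 80% power) reproduces with the two-sided normal approximation. With pooled proportion 0.35, n = [1.96 × √(2 × 0.35 × 0.65) + 0.8416 × √(0.6 × 0.4 + 0.1 × 0.9)]² / 0.5² = (1.322 + 0.483)² / 0.25 = 13.0, taken up to 14. This figure does not concern rejection, so what follows is illustrative.

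**Inputs.** From the protocol: 20 per arm (40 patients, 1:1), unstratified allocation, Fisher's exact test. Assumed, because the documents give no rejection rates: prevalence of rejection at 1 month q = 20% to 50%; risk of later rejection r1 = 70% to 80% in those patients and r0 = 40% in the rest; treatment odds ratio 0.2. I read the outcome as the proportion of patients with at least one rejection finding.

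**Step 1: chance imbalance.** The number with prior rejection in each arm is taken as Binomial(20, q).

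| q | P(arms differ by 4 or more patients) |
|---|---|
| 20% | 0.164 |
| 30% | 0.226 |
| 40% | 0.258 |
| 50% | 0.268 |

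**Step 2: effect on the crude difference, no treatment effect.** A 4-patient imbalance shifts the expected difference by (4/20) × (r1 − r0): 0.2 × 0.3 = 6 points, or 0.2 × 0.4 = 8 points. Over all randomisations the shift has SD (r1 − r0) × √(2q(1 − q)/20). The standard error of the crude difference is √(2p(1 − p)/20), with p = q·r1 + (1 − q)·r0. The share of outcome variance explained is q(1 − q)(r1 − r0)² / [p(1 − p)].

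| q; r1 vs r0 | p | SD of shift | SE of crude difference | Variance explained |
|---|---|---|---|---|
| 20%; 70% vs 40% | 46% | 3.8 points | 15.8 points | 6% |
| 30%; 80% vs 40% | 52% | 5.8 points | 15.8 points | 13% |
| 50%; 80% vs 40% | 60% | 6.3 points | 15.5 points | 17% |

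The shift is one component of the standard error, not an addition to it.

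**Step 3: planned test against stratified test.** Simulated power at 20 per arm, two-sided Fisher's exact test against the exact Cochran-Mantel-Haenszel test stratified by the 1-month result, odds ratio 0.2:

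| q; r1 vs r0 | Fisher | Stratified exact | Gain |
|---|---|---|---|
| 20%; 70% vs 40% | 45% | 49% | 4 points |
| 30%; 80% vs 40% | 41% | 50% | 9 points |
| 50%; 80% vs 40% | 39% | 52% | 13 points |
| Baseline not prognostic (30%; 40% in both) | 42% | 45% | 3 points |

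Repeat simulations move single figures by up to about two points. The last row shows that about 2 to 3 points of each gain come from Fisher's conservatism. The part due to baseline information is therefore about 1 to 2, 6 to 7 and 10 to 11 points. With no treatment effect, type I error is about 2% for Fisher and no more than about 3.5% for the stratified test.

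**Step 4: timing and carry-over.** Observation starts at randomisation, and the follow-up bronchoscopy is 2 to 3 weeks after the 1-month one. The section on airway surveillance then lists three bronchoscopies 3 to 4 weeks apart, with clearance, lavage and endobronchial biopsy; it names no transbronchial biopsy there. Rejection surveillance resumes afterwards. If the three run on from the follow-up bronchoscopy, they end 2 + 3 × 3 = 11 to 3 + 3 × 4 = 15 weeks after the 1-month biopsy. Bronchoscopies done as clinically indicated could bring a transbronchial biopsy sooner. Carry-over is possible, but its frequency cannot be worked out from the documents.

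**The case against.** An unadjusted intention-to-treat comparison is valid in a randomised trial, and use of a baseline covariate is a choice about efficiency. Every rate used above is assumed, no passage shows that rejection at 1 month predicts later rejection, and the odds ratio of 0.2 has no source in the protocol. At the low end of the assumptions, most of the small gain is only Fisher's conservatism. All of this stands, and it limits the size of the point. It does not remove it: the reading should already exist, use of it is nearly free, and the non-prognostic case shows no loss.

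Two stronger readings are tempting, and the documents do not support them.

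- A reader might infer that rejection found at 1 month is itself counted as an outcome. It cannot be: that biopsy precedes randomisation, and the 12 months start at randomisation. Only persistence or recurrence on a later biopsy could enter the count, and the plan is silent on it rather than stating that it counts.
- A reader might infer that chance imbalance biases the comparison. It does not: over all randomisations the planned test keeps its type I error, at about 2%. Imbalance affects the estimate in a given trial and adds to its variance.

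**Conclusion.** The point holds as one of efficiency. The plan should have a baseline reading of a primary outcome and uses it neither in allocation nor in analysis. If 20% to 50% of patients have rejection at 1 month, the arms differ by 4 or more such patients in 16% to 27% of trials. If later risk is 70% to 80% against 40%, and the odds ratio is 0.2, the stratified exact test gains 4 to 13 points of power over the planned test, 2 to 3 of them unrelated to the baseline result. The size rests wholly on these assumptions; the direction needs only that the 1-month result has some prognostic value.

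The missing rule on new episodes is a secondary, definitional gap. It merits a sensitivity analysis, with no claim that carry-over is common.

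**What to change.** 1. Record the 1-month transbronchial biopsy result (rejection yes or no) as a baseline variable, and state how a missing or inadequate reading is handled.
2. For the rejection outcome, replace the unstratified Fisher's exact test with an exact Cochran-Mantel-Haenszel test stratified by this result, keeping the intention-to-treat groups.
3. Add a sensitivity analysis restricted to new rejection after randomisation, with the rule for new against unresolved written in advance and applied to the biopsies available. The protocol defines no rejection grade and schedules no biopsy to establish clearance, so the rule must work without these.

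The cost is one field from an existing pathology report and slightly more analysis work. No biopsy, visit or patient is added. In the simulated case where the 1-month result has no prognostic value, there is no loss of power.
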